# 9.3 Analysis of Primary Endpoint

Dose escalation decisions and MTD are estimated through the rules specified in section 9.1.1. DLT rate at each dose level will be calculated along with the Fisher's exact confidence interval at 95% confidence level. AE, SAE and AE of special interests will be summarized by descriptive statistics to evaluate long-term safety.

# 9.4 Analysis of Secondary Endpoints

Change in serial PSA, PSA velocity and testosterone levels from baseline throughout the 90-day treatment period will be represented by longitudinal profiles and analyzed by mixed effects model. Baseline is defined as the last non-missing PSA measurement prior to administrating Epidiolex. PSA and testosterone levels may be categorized and summarized by response rates with confidence intervals. Patients who are DLT evaluable, have baseline measurement and have at least one post-baseline measurement will be included in the analysis of secondary endpoints.

The health-related quality of Life (EORTC QLQ-C30 and QLQ-PR25) collected longitudinally will be analyzed using appropriate linear models for repeated measures data.

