- 3.2.2 Any radiological evidence of metastatic disease (determined by standard of care CT scans of abdomen. pelvis, chest, whole body bone scan or Axium PET/CT scan). Questionable lesions on bone scan will be confirmed by standard of care methods such as plain X-rays or Axium PET/CT scan, if not previously performed.
- 3.2.3 Receipt of prior cytotoxic chemotherapy for recurrent prostate cancer
- 3.2.4 Use of androgen deprivation therapy (for example, bicalutamide, flutamide, niluamide, or leuprolide acetate) concurrently or within the previous 3 months.
- 3.2.5 Uncontrolled intercurrent illness such as active infections. Other illnesses will be evaluated and eligibility status determined at the discretion of the treating physician and the investigator.
- 3.2.6 Psychiatric illness/social situations that would limit compliance with study requirements.
- 3.2.7 Concomitant use of Valproate or Clobazam.
- 3.2.8 Concurrent use of over-the-counter CBD oil, Marinol or marijuana is not permitted. Patients with a history of current over-the-counter CBD oil, Marinol or marijuana use for any reason are eligible only if they do the following:
- complete a one-week washout period prior to study initiation
- refrain from non-study related CBD oil, Marinol or marijuana use while on-study
- 3.2.9 Treatment with sensitive substrates of CYP2C19 inhibitors should not be taken within 14 days prior to first dose of study treatment and for the duration of study.

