The secondary endpoints include assessment of biochemical response via serial PSA and serial testosterone levels, and health-related quality of life (as assessed by the EORTC QLQ C-30 and PR-25).

The correlative endpoint includes CBD receptor 1 and 2 expression levels.

Sample Size/Accrual Rate

We plan to enroll up to 9 DLT evaluable patients for dose escalation to establish the MTD.

Once we have established the MTD, we will begin treating 6 to 9 more patients at the MTD level in an expansion cohort to confirm safety and explore evidence of efficacy of the study treatment. The number of patients to be enrolled in expansion cohort depends on the number of non-DLT evaluable patients in the dose escalation part of the study. If all patients in the dose escalation part of the study are DLT evaluable, we will have enroll 9 more patients, otherwise, we will subtract the number of non-DLT evaluable patients from expansion cohort. The total sample size for this study is 18 (enrolled) patients with about 12 patients treated at the MTD.

Analysis of Primary Endpoint

The dose escalation and MTD will be determined by the posterior distribution of Pr(DLT) estimate [41]. The target toxicity probability is set at 30%. Safety and tolerability of Epidiolex will be monitored and assessed. AE counts will be summarized by descriptive statistics.

Analysis of Secondary Endpoints

Change of PSA and testosterone levels from baseline throughout the 90-day treatment period will be represented by longitudinal

profiles and analyzed by mixed effects model. Baseline is defined as the last non-missing PSA measurement prior to administrating study drug. PSA and testosterone levels may be categorized and summarized by response rates with confidence intervals.

The Quality of Life scores collected longitudinally will be analyzed using appropriate linear models for repeated measures data.

Analysis of Correlative Endpoints

Post-hoc analyses will be conducted on correlative endpoints with appropriate statistical methods depending on distribution and availability of collected data.

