## **Attachments**

#### **Research Procedures**

Describe how the research will be conducted.

- What experience will study participants have?
- What will study participants be expected to do?
- · How long will the study last?
- Outline the schedule and timing of study procedures.
- Provide visit-by-visit listing of all procedures that will take place.
- · Identify all procedures that will be carried out with each group of participants.
- Describe deception and debrief procedures if deception is involved.

Differentiate between procedures that involve standard/routine clinical care and those that will be performed specifically for this research project. List medications that are explicitly forbidden or permitted during study participation.

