## Pre study screening

- · Quality of Life survey
- · Informed consent discussed and signed
- · Demographic information given
- One blood draw for PSA test and total testosterone as a standard part of treatment
- Imaging scans done and the results assessed to see if the cancer has gotten worse.
- o PET or PET/CT scan at the PI's discretion
- o Bone scan at the PI's discretion
- o CT chest, abdomen, pelvis scans at the PI's discretion
- o MRI of the pelvis
- Urine THC screening test
- · EKG a test that measures the heartbeat.
- CBC: A routine blood test used to measure the ratios of different blood cell counts to see if any are out of alignment
- CMP: A routine blood test used to examine overall metabolism and identify any potential problems
- · Venipuncture for the blood tests described above
- Concomitant Medications where the doctor will assess any current medications to make sure nothing will have side effects with the Epidiolex.
- · Medical History
- · Height determined
- · Physical exams with vitals determined and ECOG performance evaluation
- · ECOG performance evaluation
- Archival tissue collection

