#### Day 1 Expidiolex administration

- · Administration of epidiolex
- Assessment of the disease progression
- · CBC: A routine blood test used to measure the ratios of different blood cell counts to see if any are out of alignment
- · CMP: A routine blood test used to examine overall metabolism and identify any potential problems
- · Possible Physical exam if your doctor determines it is needed
- · ECOG performance evaluation at the discretion of the PI.

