## Day 30-60-90 Expidiolex administrations

- · Administration of epidiolex
- · Evaluation of any symptoms known as adverse events
- Evaluating dose level based on symptoms
- · Making sure you are following instructions
- · One blood draw for PSA test and total testosterone as a standard part of treatment
- · All the above scans can be repeated per NCCN guidelines or more often as clinically indicated by suspected disease progression.
- o PET or PET/CT scan at the PI's discretion
- o Bone scan at the PI's discretion
- o CT chest, abdomen, pelvis scans at the PI's discretion
- o MRI of the pelvis
- Assessment of the disease progression
- EKG a test that measures the heartbeat.
- · CBC: A routine blood test used to measure the ratios of different blood cell counts to see if any are out of alignment
- · CMP: A routine blood test used to examine overall metabolism and identify any potential problems
- · Venipuncture for the blood tests described above
- Concomitant Medications where the doctor will assess any current medications to make sure nothing will have side effects with the Epidiolex.
- Physical exams with vitals determined and ECOG performance evaluation

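### The available schedule lists no Day 1 PSA or testosterone draw and the baseline rule sets no maximum sample age, so untreated PSA growth before dosing can count as on-treatment change

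*Combined protocol and SAP*

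**What the plan says.** Section 9.4 of the SAP analyses "Change in serial PSA, PSA velocity and testosterone levels from baseline throughout the 90-day treatment period" by longitudinal profiles and a mixed effects model, and allows the levels to be categorised into response rates without giving a threshold. Its baseline rule is "Baseline is defined as the last non-missing PSA measurement prior to administrating Epidiolex". The Study Design part of the IRB application has the same rule: "Baseline is defined as the last non-missing PSA measurement prior to administrating" study drug. Neither version limits how old the sample may be, and neither names testosterone.

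The schedule comes from the Research Procedures part of the IRB application:

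- Under Pre study screening: "One blood draw for PSA test and total testosterone as a standard part of treatment". No window in days before first dose is given.
- Under "Day 1 Expidiolex administration": dosing, a progression assessment, CBC, CMP, and physical exam and ECOG at discretion. No PSA or testosterone is listed.
- Under "Day 30-60-90 Expidiolex administrations": PSA and testosterone are drawn again.

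Inclusion criterion 3.1.2 requires a PSA increase shown at two timepoints at least 4 weeks apart. Criterion 3.2.8 lets current users of non-study CBD oil, Marinol or marijuana enter if they "complete a one-week washout period prior to study initiation". It does not tie that week to the screening draw.

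**The concern.** If the schedule is followed as listed, the last PSA before drug is the screening value. These men are enrolled because their PSA is rising, so it can be expected to keep rising until the first dose. That growth is then reported as change on treatment. The trial has one arm, so nothing cancels it, and the amount differs between men according to their gap and doubling time. With 18 patients planned (section 9.2), such differences will not reliably average out.

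Change in PSA, PSA velocity and testosterone is the plan's measure of biochemical response (section 9.1.2), and the expansion cohort is meant in part to look for efficacy. The bias runs against the drug and could hide a modest effect.

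Two smaller points go with it. A man using a non-study cannabinoid product may have his screening PSA drawn before or during washout, which could bias his change in either direction. And testosterone has no stated baseline.

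**Working it through.** The documents give no screening window, doubling time or expected PSA effect, so there is no figure of theirs to reproduce. The size below rests on assumed ranges.

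**Inputs**
- On-treatment draws at Days 30, 60 and 90: IRB application, Research Procedures. Day 90 is taken as 90 days after first dose.
- g, days from screening draw to first dose: not stated; assumed 0 to 42. A gap is plausible: a man who stops a restricted product at screening must wait one week (3.2.8) or 14 days (3.2.9).
- DT, PSA doubling time: not stated; assumed 3 to 24 months, at 30.4375 days per month.
- Drug effect: none, so that all change is untreated growth.

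**Formulas** (exponential growth)
- Growth before dosing = 2^(g/DT) − 1
- True Day 90 change from first dose = 2^(90/DT) − 1
- Apparent Day 90 change from screening = 2^((g+90)/DT) − 1

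Example, DT 6 months (182.625 days) and g = 28: growth before dosing 2^(28/182.625) − 1 = 11.2%; true change 2^(90/182.625) − 1 = 40.7%; apparent change 2^(118/182.625) − 1 = 56.5%.

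**Growth before dosing**

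| DT | g = 14 | g = 28 | g = 42 |
|---|---|---|---|
| 3 months | 11.2% | 23.7% | 37.6% |
| 6 months | 5.5% | 11.2% | 17.3% |
| 12 months | 2.7% | 5.5% | 8.3% |
| 24 months | 1.3% | 2.7% | 4.1% |

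**Day 90 change with no drug effect** (g = 0 is the true change)

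| DT | g = 0 | g = 14 | g = 28 | g = 42 |
|---|---|---|---|---|
| 3 months | +98.0% | +120.2% | +144.9% | +172.4% |
| 6 months | +40.7% | +48.4% | +56.5% | +65.0% |
| 12 months | +18.6% | +21.8% | +25.1% | +28.5% |
| 24 months | +8.9% | +10.4% | +11.8% | +13.3% |

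**Share of the log change that predates dosing.** This does not depend on DT. At Day 90 it is g/(g+90): 14/104 = 13.5%, 28/118 = 23.7%, 42/132 = 31.8%. At Day 30 it is g/(g+30): 14/44 = 31.8%, 28/58 = 48.3%, 42/72 = 58.3%. The early readings suffer most.

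**Response rates.** A true 50% fall from the Day 1 level appears as 0.5 × 2^(g/DT) − 1. With g = 28 that is −38.2% (3 months), −44.4% (6), −47.3% (12) and −48.7% (24). A 50% cut-off is illustrative only, since the plan sets none.

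**The case against.** The strongest objection is that the visit list is an answer on an IRB form, not the study calendar. The form's prompt is "Provide visit-by-visit listing of all procedures that will take place", but a prompt does not show that the answer is complete, and this one has gaps. The quality-of-life survey appears only at screening, yet section 9.4 analyses it longitudinally. Urinalysis is named as a safety measure under Records, Privacy, and Confidentiality, but no visit lists one apart from the urine THC screen. The application refers to a fuller clinical protocol, of which only section 9 is available. This stands: a reader might infer that no Day 1 PSA is ever drawn, but the documents show only that none is listed.

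The baseline rule would also accept a pre-dose Day 1 or routine-care sample if one were taken. That is true, but none is scheduled. The Day 1 progression assessment does not fill the gap, because the Day 30-60-90 list shows that assessment and the PSA draw as separate items.

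Slow doublers lose little, and the Background describes a usually long natural history. This also stands, and is why the tables run to 24 months.

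A mixed model on actual draw dates would limit the distortion of PSA velocity. The plan does not specify one, and change from baseline would still span the pre-dose interval.

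The washout point is only a possibility: the start of the study is not defined, the number of users is unknown, and screening includes a urine THC test.

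Finally, a Day 1 baseline leaves most of the untreated growth in place (+40.7% at a 6-month doubling time). It removes an avoidable error but does not replace a control arm.

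**Conclusion.** The point holds as a defect in the baseline definition and the available schedule, for secondary endpoints only. With a 28-day gap and no drug effect, the Day 90 change is overstated by about 47 percentage points at a 3-month doubling time (144.9 − 98.0), 16 at 6 months (56.5 − 40.7), 6 to 7 at 12 months (25.1 − 18.6) and 3 at 24 months (11.8 − 8.9). The gap, the doubling times and exponential growth are assumptions; if screening and Day 1 coincide the bias is zero.

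Three stronger readings are not supported. The growth argument does not extend to testosterone, where the defect is the missing baseline definition. The documents do not show that any man's baseline was in fact taken on a non-study cannabinoid product. And nothing here touches the DLT rate or the MTD.

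**What to change.** First confirm against the full study calendar whether PSA and testosterone are drawn on Day 1. If they are not:

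- Add PSA and total testosterone to the Day 1 blood work, drawn before the first dose.
- In section 9.4, define that sample as baseline for both assays. Allow the screening value as back-up only within a stated maximum age and only if drawn after any washout.
- Analyse log PSA by actual draw date, with time measured from first dose.
- Keep the two PSA values that qualified the man for entry out of the main mixed model. They were selected for showing an increase, so they tend to steepen the pre-treatment slope, and regression to the mean could then look like drug benefit. State whether the screening draw may serve as one of them.

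The cost is two assays per patient, on a day when CBC and CMP are already taken, and SAP wording. For any man already treated without a Day 1 sample, report the gap between the baseline draw and first dose beside his PSA change.

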# 9.5 Analysis of Correlative Endpoints

Post-hoc analyses will be conducted on correlative endpoints with appropriate statistical methods depending on distribution and availability of collected data.
